## 8.6 Treatment Compliance

Compliance (%) will be calculated as:

Compliance = (Number of Immunizations Received/ Expected Total Immunizations) \* 100.

#### Example 1

[figure not shown]
If a subject received 3 of the 4 injections: Compliance = (3/4)\*100 = 75%.

#### 8.7 Treatment Exposure

Duration of Exposure (days) will be calculated as:

Duration of Exposure = Date of Last Administration of Study Vaccine – Date of First Administration of Study Vaccine + 1.

of

## 8.8 Treatment Emergent Adverse Event

A treatment emergent adverse event (TEAE) is defined as:

- any AE that has an onset on or after the first dose of investigational product
- or any pre-existing condition that has worsened on or after the first dose of investigational product
- or any AE that starts prior to the end of the designated follow-up period, i.e. 24 weeks (6 months) after the end of the treatment period.

If applicable, the assessment of whether or not an AE is treatment emergent should include both the date and time relative to the first administration of study vaccine.

#### Example 1

Subject	Date of First Injection	AE Start Date	AE Stop Date	TEAE?
100101 NB. AE stopped p	16-Oct-2019 rior to the first administration of	14-Sep-2019 f vaccine, not TEAE.	15-Oct-2019	No
Example 2				
Subject	Date of First Injection	AE Start Date	AE Stop Date	TEAE?
100101 NB. AE started aft	16-Oct-2019 er the first administration of vad	18-Oct-2019 ccine, TEAE.	21-Oct-2019	Yes

Please refer to SAP Section 8.11, below for how to handle partial or missing dates in the assessment of whether or not an event is a TEAE.

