5.3.5.2 Adverse Events

All adverse events (AEs) will be coded using the most up-to-date version of the Medical Dictionary for Regulatory Affairs (MedDRA). As AEs are collected starting from the moment of the ICF signature, AEs and treatment-emergent adverse events (TEAEs) will be discriminated. A TEAE is defined as any AE that has an onset date/time on or after the first dose of investigational product, or any pre-existing condition that has worsened on or after the first dose of investigational product.

Overview of AEs will be given in terms of number and percentage of subjects per dose group experiencing:

- o AEs
- o SAEs
- Severe adverse events
- Adverse drug reactions
- AEs leading to withdrawal
- o Deaths

AEs will also be summarized by System Organ Class and Preferred Term, according to severity (mild, moderate, severe) and according to relationship to drug.

Most frequent AEs will be presented per dose group in bar charts and time to first SAE will be presented graphically.

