## 8.11 Handling of Partial or Missing Dates

For the purpose of calculating durations there will be no imputations made for partial or missing dates. Where duration of an event is calculated based on actual dates and any of the dates used in the computational algorithm are partial or missing, the duration will also be missing.

For the purpose of assigning medical histories as 'past or current', AEs as 'treatment-emergent' and therapies as 'prior or concomitant' (partially) missing start and stop dates will not be imputed.

In general, medical histories will be considered current, unless there is evidence in the (partial) dates available that the medical condition stopped prior to the first administration of study vaccine. The same rules will be applied to partial or missing AD diagnosis dates.

#### Example 1

Example	Medical History				
Subject	Date of First Injection	Start Date	Stop Date	Past/Current	
100101	16-Oct-2019	14-Sep-2019	xx-Oct-2019	Current	
NB. Month of stop date is the same as the month of the first injection so medical history is assumed to be current.					

#### Example 2

		Medical H	istory	
Subject	Date of First Injection	Start Date	Stop Date	Past/Current
100101	16-Oct-2019	xx-Sep-2019	xx-xxx-2019	Current
NB. Year of stop date is the same as the year of the first injection so medical history is assumed to be current.				

#### Example 3

		Medical H	istory	
Subject	Date of First Injection	Start Date	Stop Date	Past/Current
100101	16-Oct-2019	14-Sep-2019	XX-XXX-XXXX	Current
NB. Stop Date missing and medication not checked as ongoing, so medical history is assumed to be current.				

#### Example 4

		Medical H	listory	
Subject	Date of First Injection	Start Date	Stop Date	Past/Current
100101	16-Oct-2019	xx-Oct-2019	15-Oct-2019	Prior
NB. Although start date partial, stop date is prior to the date of the first injection, so medical history is assumed to be past.				

In general, an AE will be considered treatment-emergent, unless there is evidence in the (partial) dates available that it was not treatment-emergent. In particular, in case of missing start dates of AEs, these will be considered treatment-emergent, unless the stop date of the AE is prior to the first administration of study vaccine. In the case of partially missing start dates, the AE will be considered treatment-emergent, unless the information from the partial dates clearly shows that the AE was not treatment-emergent.

#### Example 1

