Subject	Date of First Injection	AE Start Date	AE Stop Date	TEAE?	
100101	16-Oct-2019	14-Sep-2019	xx-Sep-2019	No	
NB. Month AE stopped is prior to the month of the first injection so AE is not TEAE.					

#### Example 2

Subject	Date of First Injection	AE Start Date	AE Stop Date	TEAE?
100101	16-Oct-2019	xx-Oct-2019	xx-Oct-2019	Yes
NB. Month of A	E start and stop is the same as th	e month of the first injec	tion so AE assumed to be T	FEAE.

In general, medications will be considered concomitant, unless there is evidence in the (partial) dates available that it was stopped prior to the first administration of study vaccine.

#### Example 1

		Prior/Concomitan	t Medication	
Subject	Date of First Injection	Start Date	Stop Date	Prior/Concomitant
100101	16-Oct-2019	14-Sep-2019	xx-Oct-2019	Concomitant
NB. Month of stop date is the same as the month of the first injection so medication is assumed to be concomitant.				

#### Example 2

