#### 11.5.1 Adverse Events

All adverse events (AEs) will be coded using the most up-to-date version of the MedDRA dictionary. As AEs are collected starting from the moment of the Informed Consent Form (ICF) signature, AEs and

treatment emergent adverse events (TEAEs) will be discriminated. Please refer to Section 8.8 for the definition of TEAEs.

An overview of AEs and TEAEs will be given in terms of the number and percentage of subjects and number of AEs and TEAEs per treatment group (and overall) for the Safety Population within each of the following categories:

- AEs
- TEAEs
- Serious AEs (SAEs)
- Serious TEAEs
- Severe adverse events
- Severe TEAEs
- Adverse drug reactions
- Serious adverse drug reactions
- AEs leading to discontinuation of study treatment
- AEs leading to discontinuation from the study
- TEAEs leading to discontinuation from the study
- AEs with an outcome of death
- TEAEs with an outcome of death

[TFL Shell Table 14.3.2.1]

Selected TEAE categories from above will also be summarized by MedDRA SOC and PT [TFL Shell Table 14.3.2.2, 14.3.2.3, 14.3.2.4, 14.3.2.5, 14.3.2.6, 14.3.2.7, 14.3.2.8], according to severity (mild, moderate, severe) [TFL Shell Table 14.3.2.9] and according to relationship to drug [TFL Shell Table 14.3.2.10].

[figure not shown]
Most frequent TEAEs will be presented by Treatment Group in a Table [TFL Shell Table 14.3.2.11] and a bar chart [TFL Shell Figure 14.3.1], where most frequent TEAEs are defined events which occur in at least 10% of subjects in any treatment group. Time to first SAE since first injection (in days) will be presented graphically as a bar chart per cohort with subjects as individual points [TFL Shell Figure 14.3.2].

All AEs [Non-Injection Site Reactions (ISR) and ISRs] will be listed [TFL Shell Listing 16.2.7.1 to 16.2.7.6.3].

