## 12.0 Changes from the Analysis Planned in the Protocol

Due to the COVID-19 pandemic a notification of an Urgent Safety Measure (USM) for a change to protocol study procedures, effective immediately, was submitted to FIMEA on **01-Apr-2020** and Finnish EC (TUKIJA) on **03-Apr-2020**. A protocol amendment following the USM including the below changes was submitted to FIMEA on **17-Apr-2020** and TUKIJA on **24-Apr-2020**:

- Replacement of Visit 5 (Week 24) and Visit 6 (Week 26) by remote visits in 7 of 8 Sub-cohort 1.1 subjects. As a consequence, the third immunization, as well as procedures and assessments requiring the subjects to travel at Visit 5 (Week 24) and Visit 6 (Week 26) were cancelled.
- Cancellation of the third phone call (P3), usually performed 48-72 hours after the third immunization. This change is impacting 7 of 8 subjects who have not had their immunization at Visit 5 (Week 24) prior to the at-risk period.

Due to the changes presented above IA #2 Sub-cohort 1.1 at Week 50 will be executed as follows:

- Individual data (listings and individual figures) will not be presented for IA #2 Sub-cohort 1.1 Week 50.
- Aggregate data (summary tables and figures) will be provided for all timepoints (up to Week 50) except the timepoints where the visits were missed by 7 of 8 subjects in Sub-cohort 1.1 for which we will have only 1 value (i.e. Visit 5 Week 24 and Visit 6 Week 26).

Footnotes will be included to all outputs affected by the selection criteria as given below:

• Aggregate data outputs: "Note: Aggregate data is provided for all visits except those missed by 7 out of 8 subjects in Sub-cohort 1.1 (Visits 5 and 6)."

In certain cases, where subjects missed any visit or dropped out from the study, IA will be executed as follows:

[figure not shown]
- If there is a risk of unblinding individual data (listings and individual figures) will be presented only up until the missed visit or data for those subjects will not be included.
- Aggregate data (summary tables and figures) will be provided for all timepoints

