Table 14.2.9.2.1 Anti-CRM IgG (AU/mL) titers, in Serum – Responder Analysis (Per Protocol Population)			Х
Table 14.2.9.3 Anti-CRM IgG (AU/mL) titers, in serum, Peak and Area Under the Curve (Intention-to-Treat Population) *		X 	Х
Table 14.2.9.3.1 Anti-CRM IgG (AU/mL) titers, in Serum, Peak and Area Under the Curve (Per Protocol Population)			Х
Table 14.2.9.4 Key Antibody Ratios, in Serum, and Change from Baseline (Intention-to-Treat Population)			Х
Table 14.2.9.4.1 Key Antibody Ratios, in Serum, and Change from Baseline (Per Protocol Population)			Х
Table 14.2.10.1.1 Summary of Actual Value and Change from Baseline in AD Biomarkers (in Plasma) by Time Point (Intention-to-Treat Population)			х

 Not applicable to Cohort 2 subjects.

 Not applicable to Cohort 1 subjects.

Statistical Analysis Plan

MAIN Statistical Analysis Plan	Cohort 1 Interim Analysis (IA1)	Cohort 1 IA2 to IA7 Cohort 2 IA1 to IA6	Final Analysis
Table 14.2.10.1.1.1 Summary of Actual Value and Change from Baseline in AD Biomarkers (in Plasma) by Time Point (Per Protocol Population)			x
Table 14.2.10.1.2 Summary of Actual Value and Change from Baseline in AD Biomarkers (in CSF) by Time Point (Intention-to-Treat Population)			х
Table 14.2.10.1.2.1 Summary of Actual Value and Change from Baseline in AD Biomarkers (in CSF) by Time Point (Per Protocol Population)			Х
Table 14.2.10.1.2.2 Summary of Actual Value of AD Biomarkers for Eligibility (in CSF) by Time Point (Intention-to-Treat Population)			Х
Table 14.2.10.1.2.3 Summary of Actual Value of AD Biomarkers for Eligibility (in CSF) by Time Point (Per Protocol Population)			Х
Table 14.3.2.1 Overall Summary of Adverse Events and Treatment-Emergent Adverse Events (Safety Population)			Х
Table 14.3.2.2 Treatment-Emergent Adverse Events by System Organ Class and Preferred Term (Safety Population)			Х
Table 14.3.2.3 Serious Treatment-Emergent Adverse Events by System Organ Class and Preferred Term (Safety Population)			Х
Table 14.3.2.4 Severe Treatment-Emergent Adverse Events by System Organ Class and Preferred Term (Safety Population)			Х
Table 14.3.2.5 Adverse Drug Reaction Events by System Organ Class and Preferred Term (Safety Population)   Table 14.3.2.6 Treatment-Emergent Adverse Events Leading to Discontinuation of Study Treatment by System Organ Class and Preferred Term (Safety Population)   Term (Safety Population)			X

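### The third TEAE limb in SAP 8.8 has no lower time bound, so an AE that starts in screening and is ongoing and unchanged at the first dose counts as treatment-emergent, contrary to protocol 5.3.5.2

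*SAP*

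**What the plan says.** Protocol 5.3.5.2 gives the definition in two parts. The first is "A TEAE is defined as any AE that has an onset date/time on or after the first dose of investigational product"; the second is worsening of a pre-existing condition on or after that dose. There is no third part.

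SAP 8.8 repeats both parts and adds a third bullet, also joined by *or*: "or any AE that starts prior to the end of the designated follow-up period", that period being 24 weeks after the end of treatment. The section then says that date and time relative to the first administration should be used where applicable, and gives two examples. Example 1 (onset 14-Sep-2019, stop 15-Oct-2019, first injection 16-Oct-2019) is not a TEAE, for the stated reason that it stopped before the first injection. Example 2 starts after the first injection and is a TEAE.

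SAP 8.11 deals with missing and partial dates. An AE with a missing start date is a TEAE "unless the stop date of the AE is prior to the first administration of study vaccine". One with a partial start date is a TEAE "unless the information from the partial dates clearly shows that the AE was not treatment-emergent". Its first AE example has a complete pre-dose start date, but the reason given for exclusion is again the stop date: "NB. Month AE stopped is prior to the month of the first injection so AE is not TEAE".

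SAP 11.5.1 notes that AEs are collected from consent, says that AEs and "treatment emergent adverse events (TEAEs) will be discriminated", and refers to 8.8 for the definition. SAP 12.0, on changes from the protocol analysis, opens with "Due to the COVID-19 pandemic a notification of an Urgent Safety Measure (USM) for a change to protocol study procedures" and goes on to missed-visit handling at interim analyses. It does not mention the TEAE definition.

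**The concern.** AEs are recorded from consent, and screening lasts up to 42 days (protocol 3.2.1), so the database will hold events with onset before any vaccine or placebo was given. The TEAE definition exists to keep those events out of the on-treatment tables. A limb with only an upper limit admits them: almost every recorded AE starts before follow-up ends.

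The case is realistic. Protocol 3.5.4 requires the screening lumbar puncture to be at least 3 days before dosing because post-puncture headache might interfere with AE assessment. A headache of that kind, still present but no worse at Visit 1, is exactly the event at issue.

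Safety and tolerability is a primary objective and is read from these tables. Several planned active arms have six subjects, so a single misclassified subject is visible in a group percentage.

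**Working it through.** No sample-size or event figure enters this point. The check is to apply each rule to the same set of AE histories.

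**Inputs.** First injection is 16-Oct-2019, as in the SAP examples. Follow-up runs for 24 weeks starting 2 weeks after the last administration (protocol 3.2.3). On the full schedule the last dose is at Week 48, so follow-up ends at Week 48 + 2 + 24 = 74. That is 74 × 7 = 518 days after the first injection, or 17-Mar-2021.

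**Limbs.** L1: onset on or after the first dose. L2: pre-existing condition worsened on or after the first dose. L3: onset before the end of follow-up.

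**Rules.**
- Protocol: L1 or L2.
- SAP literal: L1 or L2 or L3.
- SAP with its examples: as literal, except that an AE that stopped before the first dose is not a TEAE.
- L3 deleted: L1 or L2.
- L3 as a cap: (L1 or L2) and L3.

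**Histories.**
- A: SAP 8.8 Example 1 (onset 14-Sep-2019, stop 15-Oct-2019).
- B: onset 14-Oct-2019, stop 18-Oct-2019, not worsened.
- C: as B, but worsened after dosing.
- D: onset 18-Oct-2019 (SAP 8.8 Example 2).
- E: onset two weeks after the end of follow-up.

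| History | L1 | L2 | L3 | Protocol | SAP literal | SAP with examples | L3 deleted | L3 as cap |
|---|---|---|---|---|---|---|---|---|
| A | no | no | yes | No | Yes | No | No | No |
| B | no | no | yes | No | Yes | **Yes** | No | No |
| C | no | yes | yes | Yes | Yes | Yes | Yes | Yes |
| D | yes | no | yes | Yes | Yes | Yes | Yes | Yes |
| E | yes | no | no | Yes | Yes | Yes | Yes | **No** |

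**Reading the table.** The literal rule contradicts the SAP's own printed answer for A. Letting the examples govern repairs A but not B, because B did not stop before dosing. The rules in 8.11 for missing or partial start dates do not reach B either, since its start date is fully known. So the SAP with its examples differs from the protocol in B alone. Deleting L3 matches the protocol in all five. Turning L3 into a cap fixes B but departs from the protocol in E.

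**Outputs touched.** An event of type B enters only the TEAE outputs whose other criteria it meets. For a mild non-serious event these are Tables 14.3.2.1, 14.3.2.2, 14.3.2.9 and 14.3.2.10. If it meets the frequency rule (at least 10% of subjects in any treatment group), Table 14.3.2.11 and Figure 14.3.1 are added. In an arm of six, one subject is 1/6 = 16.7%, so a single case meets that rule. The DSMB outputs on TEAEs (Tables 4 and 4.1, Listing 1) may be affected too, but they may follow the separate DSMB SAP, which is not available here.

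**The case against.** The best defence is that nobody would apply the third limb literally. Taken at its word it makes the other two limbs redundant for any AE starting before follow-up ends, contradicts Example 1, and defeats the AE/TEAE separation in 11.5.1. Only as an upper limit do all three limbs have work to do, and the sentence on timing relative to the first administration points the same way. On that view the text is merely loose, and its absence from SAP 12.0 suggests a slip, not an undisclosed change.

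As a reading of intent this is probably right. It does not settle history B. The timing sentence names a reference point but states no exclusion, and both examples of non-TEAEs rest on the stop date although the onset was known and pre-dose. A programmer following the written rule and the examples would flag B as treatment-emergent.

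The second defence is that the effect is small, and that stands. Illnesses already present at consent are concomitant illnesses, not AEs, unless they worsen (protocol 3.4.7.1). The event must begin in screening, persist to dosing and not worsen. It can fall in any arm, the tables are descriptive, and Listing 16.2.7.1 shows every AE.

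It can also be said that history E is hypothetical, since AEs are collected only to the last follow-up visit. Protocol 4.2.2 c) does require a related SAE that comes to light later to be reported to the sponsor, but does not say that it enters the AE dataset. E therefore matters only for how a retained cap should be worded.

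**Conclusion.** The definition is wrong as written. For an AE with onset in screening that is ongoing and unchanged at the first dose, the SAP gives TEAE and the protocol gives not TEAE, and SAP 12.0 does not disclose the difference. This rests on reading the three limbs as the alternatives they are printed as, with the SAP's examples allowed to override the text where they apply.

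The number of affected AEs cannot be worked out from the documents and is probably small. The expected effect is some over-counting in descriptive TEAE tables, in any arm, traceable through the full AE listing. Whether the TEAE flag was actually programmed on the third limb is not known. The point deserves correction because it concerns the definition behind a primary safety output and the remedy is cheap, not because a large distortion is expected.

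**What to change.** Delete the third limb from SAP 8.8. The definition then matches protocol 5.3.5.2 and needs no entry in SAP 12.0.

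If an upper limit is wanted, join it to the first two limbs by *and*, tie it to the end of each subject's designated follow-up counted from the last administration (protocol 3.2.3) and not to a fixed week, and list it in SAP 12.0. Such a limit would make an SAE with later onset, reported under protocol 4.2.2 c), a non-TEAE, which the protocol definition does not.

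Add one worked example: onset 14-Oct-2019, first injection 16-Oct-2019, stop 18-Oct-2019, not worsened; not a TEAE. Then confirm that the TEAE flag is programmed on the corrected rule.

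The cost is one deleted line, one example and a check of the flag. No new data, new outputs or protocol amendment are needed. If the flag was programmed on the third limb, the TEAE outputs must be re-run.

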## 8.9 Adverse Event Relatedness

Relationship to study treatment is recorded as unrelated, unlikely related, possibly related and probably related on the eCRF. All relationships reported as unrelated or unlikely related will be categorized as "Not Related", while possibly related and probably related will be categorized as "Related" in the AE tables. AE listings will present relationship to study treatment as available in the raw data / eCRF.

## 8.10 Abnormal Laboratory Values

Clinically significant abnormal laboratory findings or other abnormal assessments that are detected after the first administration of study vaccine or that are present at baseline and worsen following the first administration of study vaccine are included as AEs or SAEs. The investigator should exercise medical and scientific judgement in deciding whether an abnormal laboratory finding is clinically significant.

## 8.11 Handling of Partial or Missing Dates

For the purpose of calculating durations there will be no imputations made for partial or missing dates. Where duration of an event is calculated based on actual dates and any of the dates used in the computational algorithm are partial or missing, the duration will also be missing.

For the purpose of assigning medical histories as 'past or current', AEs as 'treatment-emergent' and therapies as 'prior or concomitant' (partially) missing start and stop dates will not be imputed.

In general, medical histories will be considered current, unless there is evidence in the (partial) dates available that the medical condition stopped prior to the first administration of study vaccine. The same rules will be applied to partial or missing AD diagnosis dates.

#### Example 1

Example	Medical History				
Subject	Date of First Injection	Start Date	Stop Date	Past/Current	
100101	16-Oct-2019	14-Sep-2019	xx-Oct-2019	Current	
NB. Month of stop date is the same as the month of the first injection so medical history is assumed to be current.					

#### Example 2

		Medical H	istory	
Subject	Date of First Injection	Start Date	Stop Date	Past/Current
100101	16-Oct-2019	xx-Sep-2019	xx-xxx-2019	Current
NB. Year of stop date is the same as the year of the first injection so medical history is assumed to be current.				

#### Example 3

		Medical H	istory	
Subject	Date of First Injection	Start Date	Stop Date	Past/Current
100101	16-Oct-2019	14-Sep-2019	XX-XXX-XXXX	Current
NB. Stop Date missing and medication not checked as ongoing, so medical history is assumed to be current.				

#### Example 4

		Medical H	listory	
Subject	Date of First Injection	Start Date	Stop Date	Past/Current
100101	16-Oct-2019	xx-Oct-2019	15-Oct-2019	Prior
NB. Although start date partial, stop date is prior to the date of the first injection, so medical history is assumed to be past.				

In general, an AE will be considered treatment-emergent, unless there is evidence in the (partial) dates available that it was not treatment-emergent. In particular, in case of missing start dates of AEs, these will be considered treatment-emergent, unless the stop date of the AE is prior to the first administration of study vaccine. In the case of partially missing start dates, the AE will be considered treatment-emergent, unless the information from the partial dates clearly shows that the AE was not treatment-emergent.

#### Example 1

Subject	Date of First Injection	AE Start Date	AE Stop Date	TEAE?	
100101	16-Oct-2019	14-Sep-2019	xx-Sep-2019	No	
NB. Month AE stopped is prior to the month of the first injection so AE is not TEAE.					

#### Example 2

Subject	Date of First Injection	AE Start Date	AE Stop Date	TEAE?
100101	16-Oct-2019	xx-Oct-2019	xx-Oct-2019	Yes
NB. Month of A	E start and stop is the same as th	e month of the first injec	tion so AE assumed to be T	FEAE.

In general, medications will be considered concomitant, unless there is evidence in the (partial) dates available that it was stopped prior to the first administration of study vaccine.

#### Example 1

		Prior/Concomitan	t Medication	
Subject	Date of First Injection	Start Date	Stop Date	Prior/Concomitant
100101	16-Oct-2019	14-Sep-2019	xx-Oct-2019	Concomitant
NB. Month of stop date is the same as the month of the first injection so medication is assumed to be concomitant.				

#### Example 2

